8.4 Ethical Conduct of the Study.....	49
9 MANAGEMENT AND REPORTING OF ADVERSE EVENTS/ADVERSE REACTIONS	50
10 PLANS FOR DISSEMINATING AND COMMUNICATING STUDY RESULTS	51
11. REFERENCES	52
12. LIST OF TABLES	53
13. LIST OF FIGURES	53
ANNEX 1. LIST OF STAND ALONE DOCUMENTS	53
ANNEX 2. ENCEPP CHECKLIST FOR STUDY PROTOCOLS	53

PFIZER CONFIDENTIAL

LIST OF ABBREVIATIONS

Abbreviation	Definition
ARB	Angiotensin II receptor blockers
ACE	Angiotensin-converting-enzyme inhibitor
AE	Adverse event
AEM	Adverse event monitoring
AIDS	Acquired Immune Deficiency Syndrome
AF	Atrial fibrillation
ANOVA	Analysis of variance
ATC	Anatomical Therapeutic Chemical
CHA ₂ DS ₂ -VASc	C: Congestive heart failure
	H: Hypertension
	A: Age \geq 75 years
	D: Diabetes mellitus
	S ₂ : Prior Stroke or transient ischemic attack or Thromboembolism
	V: Vascular disease (peripheral artery disease, myocardial infarction, aortic plaque)
	A: Age 65–74 years
	Sc: Sex category (female sex)
CHADS ₂	C: Congestive heart failure
	H: Hypertension
	A: Age \geq 75 years
	D: Diabetes mellitus
	S ₂ : Prior Stroke or transient ischemic attack or Thromboembolism
COPD	Chronic obstructive pulmonary disease
ECR	Electronic Case Report
GEP	Good Epidemiological Practice
GPP	Good Pharmacoepidemiology Practices
HAS-BLED	H: Hypertension
	A: Abnormal renal and liver function
	S: Stroke
	B: Bleeding
	L: Labile INR
	E: Elderly
	D: Drugs or alcohol
HMO	Health Maintenance Organizations
ICD-10	10th revision of the International classification of diseases
IEA	International Epidemiological Association
IEC	Independent Ethics Committee
INR	International normalized ratio
IRB	Institutional Review Board
ISPE	International Society for Pharmacoepidemiology
ISPOR	International Society for Pharmacoeconomics and Outcomes Research
MANOVA	Multivariate analysis of variance
NI	Non- interventional
NIS	Non-interventional study
NOAC	New oral anticoagulant
NSAID	Non-steroidal anti-inflammatory drugs
NVAF	Non-valvular atrial fibrillation

PFIZER CONFIDENTIAL

Apixaban
B0661148- NON-INTERVENTIONAL STUDY PROTOCOL
Final, 10 October 2019

Abbreviation	Definition
OAC	Oral anticoagulant
SAMe-TT ₂ R ₂	S: Sex (female)
	A: Age (<60 years)
	Me: Medical history
	T: Treatment
	T: Tobacco use (within 2 years)
	R: Race (non-Caucasian)
SPSS	Statistical Package for the Social Sciences
TIA	Transient ischaemic attack
VKA	Vitamin K Antagonist
VTE	Venous thromboembolism

PFIZER CONFIDENTIAL

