7.2.2. Exclusion Criteria

Patients meeting any of the following criteria will not be included in the study:

- e) Patients with any of the following diagnoses prior to the use of the treatments of interest or index date:
 - Valvular heart disease or valve replacement – ICD-10 codes: I05, I06, I07, I08, I09, I22, I34, I35, I36, I37, I38, I39, I700, I702-I709; Q22, Q23, Q25, T82,Z95.
 - Pregnancy during the study period. ICD-10 O00-O9A
 - Diagnosis of venous thromboembolism (VTE) – ICD-10 codes: I26, I80 - I82;
- f) Individuals with a transitory diagnosis of NVAF prior to the use of the treatments of interest or index date;
- g) Exposure to more than one OAC on or after the index date, during the follow-up period.
- h) NOAC doses different from those recommended by the manufacturing laboratories.

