Leukemia	Clinical characteristic	Medical record	Yes, No

PFIZER CONFIDENTIAL

Variable	Role	Data source (s)	Operational definition
Malignant lymphoma	Clinical characteristic	Medical record	Yes, No
Peptic ulcer disease	Clinical characteristic	Medical record	Yes, No
Metastatic solid tumor	Clinical characteristic	Medical record	Yes, No
History of ischemic or hemorrhagic stroke	Clinical characteristic	Medical record	Yes, No
History of TIA	Clinical characteristic	Medical record	Yes, No
History of de tromboembolismo	Clinical characteristic	Medical record	Yes, No
Enfermedad coronaria	Clinical characteristic	Medical record	Yes, No
History of de hemorragia gastrointestinal	Clinical characteristic	Medical record	Yes, No
History of Intracranial bleeding	Clinical characteristic	Medical record	Yes, No
History of Other bleeding	Clinical characteristic	Medical record	Yes, No
Bleeding history or predisposition at start OAC treatment	Clinical characteristic	Medical record	Yes, No
INR > 60% at start OAC treatment	Clinical characteristic	Medical record	Yes, No
Use of aspirin at start OAC treatment	Clinical characteristic	Medical record	Yes, No
Use of clopidogrel at start OAC treatment	Clinical characteristic	Medical record	Yes, No
Use of NSAIDs at start OAC treatment	Clinical characteristic	Medical record	Yes, No
HASBLED at start OAC treatment	Clinical characteristic	Medical record	Score – number higher than 0
CHA2DS2-VASc at start OAC treatment	Clinical characteristic	Medical record	Score – number higher than 0
Anaemia at start OAC treatment	Clinical characteristic	Medical record	Yes, No
Stroke	Clinical outcome	Medical record	Yes, No
Time to stroke	Clinical outcome	Medical record	Date of event dd/mm/yy

Pfizer Confidential

Variable	Role	Data source (s)	Operational definition
Type of stroke	Clinical outcome	Medical record	Ischemic stroke, Haemorrhagic or not specified
Pulmonary embolism	Clinical outcome	Medical record	Yes, No
Time to pulmonary embolism	Clinical outcome	Medical record	Date of event dd/mm/yy
Gastrointestinal bleeding	Clinical outcome	Medical record	Yes, No
Time to gastrointestinal bleeding	Clinical outcome	Medical record	Date of event dd/mm/yy
Intracranial bleeding	Clinical outcome	Medical record	Yes, No
Time to Intracranial bleeding	Clinical outcome	Medical record	Date of event dd/mm/yy
Other major bleeding	Clinical outcome	Medical record	Yes, No
Time to other major bleeding	Clinical outcome	Medical record	Date of event dd/mm/yy
CCI			

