I130	Hypertensive heart and renal disease with (congestive) heart failure
I132	Hypertensive heart and renal disease with both (congestive) heart failure and renal failure
I110	Hypertensive heart disease with (congestive) heart failure

- *Peripheral vascular disease*

ICD-10	Description
I70	Atherosclerosis
I71	Aortic aneurysm and dissection
I731	Thromboangiitis obliterans [Buerger]
I738	Other specified peripheral vascular diseases
I739	Peripheral vascular disease, unspecified

PFIZER CONFIDENTIAL

ICD-10	Description
I771	Stricture of artery
I790	Aneurysm of aorta in diseases classified elsewhere
I792	Peripheral angiopathy in diseases classified elsewhere
K551	Chronic vascular disorders of intestine
K558	Other vascular disorders of intestine
K559	Vascular disorder of intestine, unspecified
Z958	Presence of other cardiac and vascular implants and grafts
Z959	Presence of cardiac and vascular implant and graft, unspecified

▪ *Dementia*

ICD-10	Description
F00	Dementia in Alzheimer's disease
F01	Vascular dementia
F02	Dementia in other diseases classified elsewhere
F03	Unspecified dementia
G30	Alzheimer's disease
F051	Delirium superimposed on dementia
G311	Senile degeneration of brain, not elsewhere classified

▪ *Cerebrovascular disease*

ICD-10	Description
G45	Transient cerebral ischaemic attacks and related syndromes
G46	Vascular syndromes of brain in cerebrovascular diseases
I60	Subarachnoid haemorrhage
I61	Intracerebral haemorrhage
I62	Other nontraumatic intracranial haemorrhage
I63	Cerebral infarction
I64	Stroke, not specified as haemorrhage or infarction
I65	Occlusion and stenosis of precerebral arteries, not resulting in cerebral infarction
I66	Occlusion and stenosis of cerebral arteries, not resulting in cerebral infarction
I67	Other cerebrovascular diseases
I68	Cerebrovascular disorders in diseases classified elsewhere
I69	Sequelae of cerebrovascular disease
H340	Transient retinal artery occlusion

▪ *Chronic pulmonary disease*

ICD-10	Description
J40	Bronchitis, not specified as acute or chronic
J41	Simple and mucopurulent chronic bronchitis
J42	Unspecified chronic bronchitis
J43	Emphysema
J44	Other chronic obstructive pulmonary disease
J45	Asthma
J46	Status asthmaticus
J47	Bronchiectasis
J60	Coalworker's pneumoconiosis
J61	Pneumoconiosis due to asbestos and other mineral fibres
J62	Pneumoconiosis due to dust containing silica

PFIZER CONFIDENTIAL

ICD-10	Description
J63	Pneumoconiosis due to other inorganic dusts
J64	Unspecified pneumoconiosis

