H: I10, I11, I12, I13, I15

Score 1 point

ICD-10	Description
I10	Essential (primary) hypertension
I11	Hypertensive heart disease
I12	Hypertensive renal disease
I13	Hypertensive heart and renal disease
I15	Secondary hypertension

A: Age \geq 75 years

Score 2 points

D: E10 a E14

Score 1 point

ICD-10	Description
E10	Insulin-dependent diabetes mellitus
E11	Non-insulin-dependent diabetes mellitus
E12	Malnutrition-related diabetes mellitus
E13	Other specified diabetes mellitus
E14	Unspecified diabetes mellitus

S2: G45.0, G45.1, G45.2, G45.3, G45.8, G45.9

Score 2 points

ICD-10	Description
G450	Vertebral-basilar artery syndrome
G451	Carotid artery syndrome (hemispheric)
G452	Multiple and bilateral precerebral artery syndromes
G453	Amaurosis fugax
G458	Other transient cerebral ischaemic attacks and related syndromes

V: I26, I82, I21- I25, I65, I70- I72, I73.1, I73.8, I73.9, I79.0, I79.2, K55.1, K55.8, K55.9, Z95.8, Z95.9

Score 1 point

ICD-10	Description
I26	Pulmonary embolism
I82	Other venous embolism and thrombosis
I21	Acute myocardial infarction
I22	Subsequent myocardial infarction
I23	Certain current complications following acute myocardial infarction
I24	Other acute ischaemic heart diseases
I25	Chronic ischaemic heart disease
I65	Occlusion and stenosis of precerebral arteries, not resulting in cerebral infarction
I70	Atherosclerosis
I71	Aortic aneurysm and dissection
I72	Other aneurysm
I731	Thromboangiitis obliterans [Buerger]
I738	Other specified peripheral vascular diseases
I739	Peripheral vascular disease, unspecified
I790	Aneurysm of aorta in diseases classified elsewhere
I792	Peripheral angiopathy in diseases classified elsewhere
K551	Chronic vascular disorders of intestine
K558	Other vascular disorders of intestine

A: Age 64-74 years

Score 1 point

Sc: Sex category (female)

Score 1

- **HASBLED score:** The HAS-BLED score will be used to analyze the risk of bleeding. The modified HAS-BLED score ranges from 0 to 8. ICD-10 diagnostic codes for each component of the index when applicable:

•

H: I10, I11, I12, I13, I15

Score 1 point

ICD-10	Description
I10	Essential (primary) hypertension
I11	Hypertensive heart disease
I12	Hypertensive renal disease
I13	Hypertensive heart and renal disease
I15	Secondary hypertension

Apixaban

B0661148- NON-INTERVENTIONAL STUDY PROTOCOL

Final, 10 October 2019

A: N03.2, N03.3, N03.4, N03.5, N03.6, N03.7, N05.2, N05.3, N05.4, N05.5, N05.6, N057, N18- N19, N25.0, Z49.0, Z49.2, Z94.0, Z99.2

Score 1 point

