Peripheral artery disease	I702 Atherosclerosis of arteries of the extremities I708 Atherosclerosis of other arteries I709 Generalised and unspecified atherosclerosis
Anaemia	D50 Iron deficiency anaemia D51 Vitamin B12 deficiency anaemia D52 Folate deficiency anaemia D53 Other nutritional anaemias D55 Anaemia due to enzyme disorders D56 Thalassaemia D57 Sickle-cell disorders D58 Other hereditary haemolytic anaemias D59 Acquired haemolytic anaemia
Congestive heart failure	I110 Hypertensive heart disease with (congestive) heart failure I130 Hypertensive heart and renal disease with (congestive) heart failure I132 Hypertensive heart and renal disease with both (congestive) heart failure and renal failure
Renal disease	B15 Acute hepatitis A B16 Acute hepatitis B B17 Other acute viral hepatitis B18 Chronic viral hepatitis B19 Unspecified viral hepatitis C22 Malignant neoplasm of liver and intrahepatic bile ducts K70 Alcoholic liver disease K71 Toxic liver disease K72 Hepatic failure, not elsewhere classified K73 Chronic hepatitis, not elsewhere classified K74 Fibrosis and cirrhosis of liver

PFIZER CONFIDENTIAL

Variable	Operacional definition ICD-10
	K75 Other inflammatory liver diseases K76 Other diseases of liver K77 Liver disorders in diseases classified elsewhere Z944 Liver transplant status
Myocardial infarction	I21 Acute myocardial infarction I22 Subsequent myocardial infarction I252 Old myocardial infarction
Peripheral vascular disease	I70 Atherosclerosis I71 Aortic aneurysm and dissection I731 Thromboangiitis obliterans [Buerger] I738 Other specified peripheral vascular diseases I739 Peripheral vascular disease, unspecified I771 Stricture of artery I790 Aneurysm of aorta in diseases classified elsewhere I792 Peripheral angiopathy in diseases classified elsewhere K551 Chronic vascular disorders of intestine K558 Other vascular disorders of intestine K559 Vascular disorder of intestine, unspecified Z958 Presence of other cardiac and vascular implants and grafts Z959 Presence of cardiac and vascular implant and graft, unspecified
TIA	G450 Vertebro-basilar artery syndrome G458 Other transient cerebral ischaemic attacks and related syndromes G451 Carotid artery syndrome (hemispheric) G459 Transient cerebral ischaemic attack, unspecified
Coronary artery disease	I20 Angina pectoris I21 Acute myocardial infarction

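### Item V of CHA2DS2-VASc gives its point for conditions outside the protocol's own definition of vascular disease

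*Combined protocol and SAP*

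**What the plan says.** The list of abbreviations spells out the vascular item as "V: Vascular disease (peripheral artery disease, myocardial infarction, aortic plaque". The only other specification is the code line in Section 7.3.1, under the covariate definitions: "V: I26, I82, I21- I25, I65, I70- I72, I73.1, I73.8, I73.9, I79.0, I79.2, K55.1, K55.8, K55.9, Z95.8, Z95.9". Any of these codes scores one point.

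Elsewhere the protocol groups some of these codes differently:

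- **Infarction.** The Charlson list in 7.3.1 and Table 2 both code myocardial infarction as I21, I22 and I25.2 only.
- **Peripheral artery disease.** Table 2 codes it as "I702 Atherosclerosis of arteries of the extremities I708 Atherosclerosis of other arteries I709 Generalised and unspecified atherosclerosis".
- **I65.** This code ("Occlusion and stenosis of precerebral arteries, not resulting in cerebral infarction") is placed under cerebrovascular disease in the Charlson index.
- **Venous thromboembolism.** Section 7.2.2 makes it an exclusion: "Diagnosis of venous thromboembolism (VTE) – ICD-10 codes: I26, I80 - I82". The exclusion applies to "Patients with any of the following diagnoses prior to the use of the treatments of interest or index date".
- **Other exclusions.** The valvular exclusion line in 7.2.2 includes I22 and ends "I39, I700, I702-I709; Q22, Q23, Q25, T82,Z95". The matching line in the abstract also includes I21.

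Table 1 lists "CHA2DS2-VASc at start OAC treatment" as a clinical characteristic taken from the medical record. Section 7.3.1 says the score serves to stratify stroke risk.

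**The concern.** A programmer who follows the code line will not produce the score that the abbreviation list describes. A patient with chronic ischaemic heart disease but no infarction, peripheral artery disease or aortic plaque scores 1 on V from the codes and 0 from the definition.

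The study is descriptive, and its first primary objective is to report demographic and clinical characteristics. The baseline risk score is therefore part of the main result. An error in how V is specified moves patients between score values, and neither a large sample nor the checks in Section 7.8 would remove it. It matters most at low scores: a man under 64 with no other risk factor and only an I25 code other than I25.2 is reported as 1 instead of 0.

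**Working it through.** **1. The plan's own range.** Section 7.3.1 gives a range of 0 to 9. Summing the item points, with the two age items mutually exclusive: C 1 + H 1 + age ≥75 2 + D 1 + S2 2 + V 1 + Sc 1 = 9. The range reproduces. V can change a patient's score by at most 1.

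**2. Code-by-code check of V.** The line holds 21 codes or categories. They are set against the abbreviation-list definition, the protocol's own groupings, and the exclusions in 7.2.2 and the abstract.

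| V codes | Protocol's label or grouping elsewhere | Within the definition of V? | Can score in an eligible patient? |
|---|---|---|---|
| I21, I22, and I25.2 within I25 | Myocardial infarction | Yes | I22 no; I21 yes under 7.2.2, no under the abstract; I25.2 yes |
| I23 | Complications after acute infarction | Yes, by its label | Yes |
| I24 | Other acute ischaemic heart disease; in no infarction list | No | Yes |
| I25 other than I25.2 | Chronic ischaemic heart disease; in no infarction list | No | Yes |
| I65 | Cerebrovascular disease (Charlson) | No | Yes |
| I72 | Other aneurysm; in neither peripheral group | No | Yes |
| I70 | Peripheral vascular disease; I70.2, I70.8, I70.9 are the peripheral artery disease row | Largely | Only I70.1 is left |
| I73.1, I73.8, I73.9, I79.2 | Peripheral vascular disease; not in the peripheral artery disease row | Plausible by label | Yes |
| I71, I79.0 | Aortic aneurysm; peripheral vascular disease group | Unclear | Yes |
| K55.1, K55.8, K55.9 | Peripheral vascular disease; not in the peripheral artery disease row | Not by the narrower row | Yes |
| I26, I82 | Venous thromboembolism | No | No |
| Z95.8, Z95.9 | Peripheral vascular disease | Not by label | No |

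Five entries should not score under 7.2.2 (I26, I82, I22, Z95.8, Z95.9). Under the abstract it is six, because I21 is added. Seven entries lie outside the definition and can still score: I24, I25 (in part), I65, I72 and the three K55 codes. All three of Table 2's peripheral artery disease codes are exclusion codes, so among eligible patients V leans more heavily on the out-of-definition codes.

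**3. Size for item V.** N = 7,500 (Section 7.5). Let p be the share of patients whose V point comes only from out-of-definition codes. The documents do not give p; 2% to 20% is an assumption.

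- Patients affected = N × p: 7,500 × 0.02 = 150; 7,500 × 0.20 = 1,500.
- Rise in the mean of V = p × 1 point: 0.02 to 0.20.

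**4. Does the total score rise?** The abbreviation list defines S2 as prior stroke, transient ischaemic attack or thromboembolism, worth 2 points. Its code line in 7.3.1 holds only G45 codes, without I63, I64 or I74. Let s be the share with a prior stroke or embolism and no G45 code (assumed 2% to 15%). Then net mean shift = p − 2s.

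| p | s | Net shift |
|---|---|---|
| 20% | 2% | 0.20 − 0.04 = +0.16 |
| 10% | 5% | 0.10 − 0.10 = 0 |
| 20% | 10% | 0.20 − 0.20 = 0 |
| 5% | 15% | 0.05 − 0.30 = −0.25 |
| 2% | 15% | 0.02 − 0.30 = −0.28 |

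The sign depends on shares that the documents do not supply.

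**The case against.** The strongest reply is that the abbreviation list is only a gloss and that 7.3.1 is the operational definition, so a wide V may be intended. Table 1 names the medical record as the source of the score, and 7.3.1 applies ICD-10 codes only where applicable, so it is unclear how far the list drives the score. No eligibility rule or prespecified cut-point uses it, and Section 7.7 rules out treatment comparison.

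These points limit the consequence. They do not remove the mismatch. The protocol states in words what V means in one place only, and the code line does not match it. If a wider item is intended, the protocol should say so. K55.x is a fair point for the other side, since the protocol twice groups it under peripheral vascular disease. It is a borderline code to be decided, not a plain error.

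Three stronger readings are tempting but unsupported:

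- **That the total stroke-risk score is inflated.** Only V is shown to be over-scored; the S2 omission works the other way and is worth twice as much per patient.
- **That venous thromboembolism inflates the score.** I26 and I82 before index are exclusion diagnoses and the score is taken at treatment start, so these entries are redundant and add almost nothing.
- **That V captures all ischaemic heart disease.** The list starts at I21. I20 (angina) is absent, although Table 2 lists it under coronary artery disease.

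**Conclusion.** The point holds for item V. Measured against the protocol's own definition, the code list gives a point for I24, I25 other than I25.2, I65 and I72, and for K55.x if the narrower peripheral artery disease row governs. The effect is at most 1 point per patient. Under the assumed 2% to 20% share it touches 150 to 1,500 of 7,500 patients and adds 0.02 to 0.20 to the mean of V. That range is an assumption, and the exclusion of Z95 may remove some patients with I25 codes.

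The net direction of the total score is not established: under the assumed shares it runs from +0.16 to −0.28. This is worth correcting because the score is a baseline characteristic under a primary objective and the correction is cheap. It does not threaten the study's design.

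**What to change.** 1. Remove I24, I25 other than I25.2, I65, I72, I26 and I82 from V.
2. Keep I21, I22, I23 and I25.2 for infarction. I23 stays because the protocol labels it a complication of infarction. Keep the peripheral artery and aortic atherosclerosis codes, and confirm that I73.x and I79.2 are meant to count, since Table 2's peripheral artery disease row omits them.
3. Decide K55.x, I71 and I79.0 explicitly against the definition of V and record the decision. Scoring V from the Table 1 peripheral vascular disease field does not avoid this, because Table 2 codes that variable with K55.x, I71 and Z95.8/Z95.9.
4. Reconcile V with the exclusion codes in the abstract and 7.2.2 (I21 in the abstract only; I22, I70.0, I70.2-I70.9 and Z95 in both). As written, these remove many patients who meet the definition of V, and the two lists differ on I21.
5. Correct the S2 list in the same edit so that it covers prior stroke and thromboembolism as defined, including I63, I64 and I74 as the protocol codes them elsewhere.
6. State whether the score is built from codes or from the chart. If the wider V is wanted, report it as a labelled sensitivity score.

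The cost is a small code-list edit with no new data, and a slightly lower reported frequency of V. Item 4 needs a decision on the exclusion lists as well.

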K272	Acute with both haemorrhage and perforation
K274	Chronic or unspecified with haemorrhage
K276	Chronic or unspecified with both haemorrhage and perforation
K280	Acute with haemorrhage
K282	Acute with both haemorrhage and perforation
K284	Chronic or unspecified with haemorrhage
K286	Chronic or unspecified with both haemorrhage and perforation
K290	Acute haemorrhagic gastritis
K625	Haemorrhage of anus and rectum
K920	Haematemesis
K921	Melaena
K922	Gastro-intestinal haemorrhage, unspecified
D62	Acute posthaemorrhagic anaemia
H356	Retinal haemorrhage
H431	Vitreous haemorrhage
H450	Vitreous haemorrhage in diseases classified elsewhere
H922	Otorrhagia
I312	Haemopericardium, not elsewhere classified
J942	Haemothorax
R04	Haemorrhage from respiratory passages
K661	Haemoperitoneum
M250	Haemarthrosis
N02	Recurrent and persistent haematuria
N938	Other specified abnormal uterine and vaginal bleeding
N939	Abnormal uterine and vaginal bleeding, unspecified
N950	Postmenopausal bleeding
R31	Unspecified haematuria
R58	Haemorrhage, not elsewhere classified
T792	Traumatic secondary and recurrent haemorrhage

- Ischemic stroke:** Patients who report the following diagnoses in the medical history during the follow-up period:

ICD-10	Description
I63	Cerebral infarction
I64	Stroke, not specified as haemorrhage or infarction

Except I63.6 Cerebral infarction due to thrombosis of cerebral veins, non-pyogenic

- Hemorrhagic stroke:** Patients presenting the following diagnosis in the medical record:

PFIZER CONFIDENTIAL

ICD-10	Description
I60	Subarachnoid haemorrhage
I61	Intracerebral haemorrhage
I62	Other nontraumatic intracranial haemorrhage

- **Systemic embolism:** Patients who report any of the following diagnoses:

ICD-10	Description
I74	Arterial embolism and thrombosis

Definition of covariates

- **Age:** Categorical variable, continues in years. It will be defined from the index date and will be used to assign patients to the following age categories:

18 - 49
 50 - 59
 60 - 69
 70 - 79
 ≥ 80 years old.

- **Charlson Index:** Charlson comorbidity index will be created during the reference period taking into account the following score:

1 point each:

- *Myocardial infarction*

ICD-10	Description
I21	Acute myocardial infarction
I22	Subsequent myocardial infarction
I252	Old myocardial infarction

- *Congestive heart failure*

ICD-10	Description
I110	Hypertensive heart disease with (congestive) heart failure

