C84	Peripheral and cutaneous T-cell lymphomas
C85	Other and unspecified types of non-Hodgkin's lymphoma
C88	Malignant immunoproliferative diseases
C90	Multiple myeloma and malignant plasma cell neoplasms
C91	Lymphoid leukaemia
C92	Myeloid leukaemia
C93	Monocytic leukaemia
C94	Other leukaemias of specified cell type
C95	Leukaemia of unspecified cell type
C96	Other and unspecified malignant neoplasms of lymphoid, haematopoietic and related tissue
C97	Malignant neoplasms of independent (primary) multiple sites

3 points each:

- *Moderate or severe liver disease*

ICD-10	Description
K704	Alcoholic hepatic failure
K711	Toxic liver disease with hepatic necrosis
K721	Chronic hepatic failure
K729	Hepatic failure, unspecified
K765	Hepatic veno-occlusive disease
K766	Portal hypertension
K767	Hepatorenal syndrome
I850	Oesophageal varices with bleeding
I859	Oesophageal varices without bleeding
I864	Gastric varices
I982	Oesophageal varices in diseases classified elsewhere

6 points each:

- *Metastatic solid tumor*

ICD-10	Description
C77	Secondary and unspecified malignant neoplasm of lymph nodes
C78	Secondary malignant neoplasm of respiratory and digestive organs
C79	Secondary malignant neoplasm of other sites
C80	Malignant neoplasm without specification of site

- *Human immunodeficiency virus (HIV)-AIDS*

ICD-10	Description
B20	Human immunodeficiency virus [HIV] disease resulting in infectious and parasitic diseases
B21	Human immunodeficiency virus [HIV] disease resulting in malignant neoplasms
B22	Human immunodeficiency virus [HIV] disease resulting in other specified diseases
B24	Unspecified human immunodeficiency virus [HIV] disease
Z21	Asymptomatic human immunodeficiency virus [HIV] infection status

One point was added to the total score of the Charlson index for each decade after the age of 50 years:

50 to 59: 1 point,

60 to 69: 2 points,

70 to 79: 3 points,

80 to 89: 4 points,

>90: 5 points.

- **CHA₂DS₂-VACs score:** The CHA₂DS₂-VACs score will be used to analyze the effect of stratification of the risk of stroke. CHA₂DS₂-VACs scores range from 0 to 9. ICD-10 diagnostic codes for each component of the index when applicable:
 - **C:** I11.0, I13.0, I13.2, I50
Score 1 point

ICD-10	Description
I110	Hypertensive heart disease with (congestive) heart failure
I130	Hypertensive heart and renal disease with (congestive) heart failure
I132	Hypertensive heart and renal disease with both (congestive) heart failure and renal failure
I50	Heart failure

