7.5. Study Size

The total population of patients treated with OAC between January 1, 2013 and June 30, 2018 was analyzed in the claim dabtabase. For the purpose of the study, it contains the information of 7,500 patients, once they were verified that they met the inclusion criteria of the study. This means that patients who start warfarin and NOACs would be included within this period. Patients who initiate NOACs within the established period and who have been exposed to warfarin before 2013 will also be included.

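### CHA2DS2-VASc age point starts at 64 in Section 7.3.1 but at 65 in the abbreviation list, and the Charlson age bands leave age 90 unassigned (minor)

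*Combined protocol and SAP*

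**What the plan says.** **CHA2DS2-VASc.** The scoring rule in Section 7.3.1 gives 1 point for "A: Age 64-74 years" and 2 points from age 75. The List of Abbreviations, expanding the same acronym, has "A: Age 65–74 years". Section 7.3.1 says that the "score will be used to analyze the effect of stratification of the risk of stroke", and Table 1 lists CHA2DS2-VASc at the start of OAC treatment among the clinical characteristics.

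**Charlson.** Section 7.3.1 says: "One point was added to the total score of the Charlson index for each decade after the age of 50 years". The bands below that sentence give 1 point for 50-59, 2 for 60-69, 3 for 70-79, then "80 to 89: 4 points". The last band gives 5 points and is written as strictly greater than 90.

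**Age.** The covariate is in years: "It will be defined from the index date and will be used to assign patients to the following age categories".

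The protocol is version 1.0 and Section 3 lists no amendments, so all of this is current text.

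**The concern.** The two CHA2DS2-VASc statements cannot both be coded. A programmer will work from the operational definition in Section 7.3.1, not from the abbreviation list, so the 64-74 band is the one likely to be used. CHA2DS2-VASc is a listed baseline variable, so it falls under the first primary objective, and it is intended for stroke-risk stratification. One extra point can move a patient to another stratum.

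The Charlson problem is a gap rather than a contradiction between two cut-offs. Age 90 is not in the 80-89 band and not above 90. What happens to these patients depends on the programmer: an if-else chain may leave them at zero, a lookup may return missing. If the result is missing, Section 7.7.1 (no imputation, observed cases only) would drop some of the oldest patients from any Charlson summary.

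**Working it through.** No sample-size, power or event figure is involved. The check is to apply each rule to every whole-year age and see where the answers differ, then to size the affected group under a stated assumption.

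**1. CHA2DS2-VASc age points, ages 18 to 105**

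| Age | Section 7.3.1 (64-74) | Abbreviation list (65-74) |
|---|---|---|
| 63 | 0 | 0 |
| 64 | 1 | 0 |
| 65-74 | 1 | 1 |
| 75 and over | 2 | 2 |

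Only age 64 differs, by one point.

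**2. Charlson age points, ages 18 to 105**

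The bands as listed are compared with the pattern that they follow: points = floor((age - 40)/10) from age 50, capped at 5. This gives 1 for 50-59, 2 for 60-69, 3 for 70-79, 4 for 80-89 and 5 from 90.

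| Age | Bands as listed | Pattern |
|---|---|---|
| 89 | 4 | 4 |
| 90 | no band | 5 |
| 91 and over | 5 | 5 |

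Only age 90 differs. Whole years is the natural reading: with fractional ages, values such as 59.5 or 89.5 would also fall between bands.

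The introductory sentence alone could be counted as four completed decades between 50 and 90. The bands, however, already give the first point at 50-59, so on the protocol's own counting age 90 earns 5.

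**3. Number of patients affected**

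- Cohort size: Section 7.5 says "it contains the information of 7,500 patients".
- Age distribution: not given. Assumption: normal, mean m from 72 to 78, SD s from 9 to 11, in any combination.
- Proportion aged a in completed years: P(a) = Φ((a + 1 - m)/s) - Φ((a - m)/s).

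Extremes over the range:

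- Age 64, lowest (m = 78, s = 9): 0.07431 - 0.05991 = 0.01440; × 7,500 = 108.
- Age 64, highest (m = 72, s = 9): 0.21835 - 0.18703 = 0.03132; × 7,500 = 235.
- Age 90, lowest (m = 72, s = 9): 0.98262 - 0.97725 = 0.00537; × 7,500 = 40.
- Age 90, highest (m = 78, s = 11): 0.88136 - 0.86234 = 0.01902; × 7,500 = 143.

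**4. Effect on cohort means**

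- CHA2DS2-VASc: 1 × 0.0144 to 1 × 0.0313, so +0.014 to +0.031 points.
- Charlson, only if unassigned is coded as zero: -5 × 0.0054 to -5 × 0.0190, so -0.027 to -0.095 points.

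**The case against.** The strongest reply is that both slips are trivial. Each touches a single year of age, cohort means barely move, subgroup incidence is exploratory, and Section 7.7 says that treatments will not be compared. No eligibility rule, outcome definition or sample size depends on either cut-off. All of this stands, and it is why the point is minor.

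A reader might infer that the protocol gives 90-year-olds no Charlson age points, or scores them 5 too low. The documents do not support that. They assign no zero; they leave the age out of a list whose own rule points to 5. The 5-point loss arises only if unassigned is coded as zero.

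A reader might also take the Charlson gap to affect a named primary result. The readable part of Table 1 has no Charlson score (some rows are redacted), and Section 7.7 as readable names no analysis that uses it. It appears only as a covariate definition, so no effect on a specific planned result can be shown.

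The HAS-BLED elderly item in the same section starts at 65, but it belongs to a different score and does not settle the CHA2DS2-VASc band. The direct evidence is the abbreviation list.

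The patient counts may also be generous. Section 7.5 describes the 7,500 as verified against the inclusion criteria, without mentioning the exclusions, and Section 7.2 makes the cohort depend on access to medical records.

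None of this removes the two defects: one item has two definitions, and one age has no band.

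**Conclusion.** The point holds as a minor inconsistency of definition. It is certain from the text that the CHA2DS2-VASc age item has two different lower limits and that a patient aged 90 in completed years fits no Charlson band.

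For CHA2DS2-VASc the error is one point per 64-year-old relative to the abbreviation list, if the score is derived from Section 7.3.1 as written. For Charlson the size depends on how an unassigned age is handled: up to 5 points per 90-year-old if set to zero, exclusion from the summary if set to missing, and nothing if the programmer applies the per-decade pattern.

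The counts of 108-235 and 40-143 rest on an assumed normal age distribution and on all 7,500 patients being analysed. They indicate scale only. The documents give no ground for saying that the study's conclusions would change.

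**What to change.** Make two wording corrections in Section 7.3.1:

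- Change the lower CHA2DS2-VASc age item to 65-74 years, to match the List of Abbreviations.
- Write the top Charlson age band as ≥90, 5 points, and state that age is in completed years at the index date.

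Make both before the scores are programmed. They need no new data and no change to design, eligibility or outcomes. The cost is the edit itself.
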